Outcomes	Function						
	Barthel Index (primary outcome)	X		X	X	X	X
	Gait speed	X		X	X		
	6-minute walk	X			X		
	Depression SCID (given if indicated by MADRS)	X					
	MADRS	X		X			
	17-item positive and negative affect scale	X	X	X		X	X
Processes	Rehabilitation intensity						
	Patient active time & actigraphy (at 20% of sessions at random)	collected each session throughout stay					
	Treatment engagement						
	Observer-rated Rehabilitation Participation Scale (at 20% of sessions at random)	collected each session throughout stay					
	Fidelity data (at 20% of session at random)	collected each session throughout stay					
	Post-Treatment Affect						
	Self-Assessment Moniker (at 20% of session at random)	collected each session throughout stay					
	Patient Satisfaction and Treatment Fidelity Survey	Collected after therapy sessions throughout stay					
	Other rehabilitation variables						
	Rehospitalization			X	X	X	X

Disposition (home, long-term care)	X		X	X	X	X
Social Participation (PROMIS Ability to Participate in Social Roles and Activities)					X	X
Instrumental Activities of Daily Living (OARS IADL)					X	X
Executive Functioning (Clock Drawing Test)	X					
Fear of Falling	X					
Readiness for Rehab	X	X				
Short Blessed Test	X					
Medical Comorbidity (CIRS-G)	X					
Barthel Index: Pre-morbid version	X					

F3 SNF Admit (Baseline) Visit

The baseline visit will take place immediately or soon after the patient consents to the study. The rater will conduct the following assessments: Barthel, 6 minute walk, gait speed, SCID, MADRS, PANAS, Disposition, Clock Drawing Test, Fear of Falling, Readiness for Rehab, CIRS-G, Barthel Index: Pre-morbid version.

F4 Day 7 Visit

The day 7 visit will take place 7 days after the patient consents to the study. The rater will conduct the following assessments: PANAS, Readiness for Rehab.

F5 Day 30 Visit

The day 30 visit will take place 30 days after the patient's date of admission to the facility. If the patient has already been discharged from the skilled nursing facility, the rater will call the patient to schedule a home visit to conduct the following assessments: Barthel, gait speed, MADRS, PANAS, Follow-up Disposition.

F6 SNF Discharge

The discharge visit will take place as close in time to the patient's discharge date as possible. The rater will conduct the following assessments at the skilled nursing facility: Barthel, 6 minute walk, gait speed, Discharge Location..

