Time course analyses will be conducted to investigate the differences between pre and post outcome measures. These analyses will be used to ascertain whether there is a statistically significant difference in change over time between the EMR group and the SOC group, controlling for baseline values. Analyses of the outcome measures for normality will be carried out. Time course analysis techniques such as mixed effects models, t test of the differences, Wilcoxon test of the differences, or ANCOVA on the differences (using baseline value as the covariate) will then be conducted, depending on the normality tests. Our favored method for the primary analysis of baseline to day 30 (i.e., pre-post treatment) effects is the ANCOVA approach, comparing the EMR and standard-of-care groups in change scores, covarying for baseline scores. This approach is recommended as the superior and most well-powered approach for examining pre-post RCT data.⁹¹ Our tests of the pilot data agreed with this: the ANCOVA approach had as much or more statistical power than other approaches (t-test, Wilcoxon, mixed-effect model) for all outcomes.

Participants will be randomized within each facility (i.e., stratified by facility) and then receive a PT/OT therapist pair who either is or is not trained/supervised in EMR based on randomization assignment. Thus participants are nested within therapists and therapists are nested within facilities. This multi-stage nested (hierarchical) design structure introduces possible correlation of participant outcomes with therapist. Such classification effects (facility/therapist) will be analyzed using Proc Nested in SAS or with the multi-level modeling available in Mplus that deals with stratification, clustering, and weighting.

We will also examine all time points to Day 90, to provide a real-world estimate of EMR and improve power to detect important secondary outcomes such as rehospitalization and institutionalization. We acknowledge these data may become somewhat naturalistic

in a rehabilitation population, given differences in length of stay, transfers to different facilities, and re-hospitalizations. Mixed effects models are the preferred method for these multiple-time-point analyses, especially as some missing data are to be expected post-discharge.⁹²

H Data Handling and Record Keeping

H1 Confidentiality and Security

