Outcomes	Function						
	Barthel Index (primary outcome)	X		X	X	X	X
	Gait speed	X		X	X		
	6-minute walk	X			X		
	Depression SCID (given if indicated by MADRS)	X					
	MADRS	X		X			
	17-item positive and negative affect scale	X	X	X		X	X

Processes	Rehabilitation intensity					
	Patient active time & actigraphy (at 20% of sessions at random)	collected each session throughout stay				
	Treatment engagement					
	Observer-rated Rehabilitation Participation Scale (at 20% of sessions at random)	collected each session throughout stay				
	Fidelity data (at 20% of session at random)	collected each session throughout stay				
	Post-Treatment Affect					
	Self-Assessment Moniker (at 20% of session at random)	collected each session throughout stay				
	Patient Satisfaction and Treatment Fidelity Survey	Collected after therapy sessions				
	Other rehabilitation variables					
	Rehospitalization		X	X	X	X
	Disposition (home, long-term care)	X	X	X	X	X
	Social Participation (PROMIS Ability to Participate in Social Roles and Activities)				X	X
	Instrumental Activities of Daily Living (OARS IADL)				X	X
	Executive Functioning (Clock Drawing Test)	X				
	Fear of Falling	X				
	Readiness for Rehab	X	X			
	Short Blessed Test	X				
	Medical Comorbidity (CIRS-G)	X				
	Barthel Index: Pre-morbid version	X				

Statistical Principles:

i. Confidence Intervals and P-Values

Level of significance is 5%

ii. Adherence and protocol deviations

Protocol Deviation:

Any alteration or modification to the IRB-approved research without prospective IRB approval. The term research encompasses all IRB-approved materials and documents including the detailed protocol, IRB application, consent form, recruitment materials, questionnaires/data collection forms, and any other information relating to the research study.

Therapist adherence and competence was tracked two times per participant.

Variables: number of EMR principles used per therapy session; PAT.

iii. Analysis Populations

Trial Population:

- i. Screening data to describe representativeness of trial sample will include age, gender, race and ethnicity.
- ii. Eligibility

Inclusion Criteria:

- a. 65 years of age and older
- b. Admitted to a skilled nursing facility for post-acute care from PT and OT for 2 weeks or more.

Exclusion Criteria:

- a. Language, visual or hearing barriers to participation (e.g. unable to communicate with research staff).

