- b. Medical illness preventing study participation or accurate data collection (e.g., highly unstable cardiac illness such that early re-hospitalization is expected; metastatic or other cancer such that hospice is recommended or survival is limited).
- c. Moderate-severe dementia (demonstrated by chart diagnosis and/or short blessed score greater than 13).
- d. Progressive neurological condition such that recovery of function is not feasible.
- e. Patient did not have the ability to walk prior to hospitalization (e.g. paraplegic).
- f. Schizophrenia or other chronic or current psychotic disorder.
- g. Patient normally resides in a long-term care facility.

- iii. Recruitment: the numbers that will be presented in a CONSORT diagram include:
 - 1. # Screened/Consented and reasons for ineligibility.
 - 2. # Randomized to EMR vs SOC.
 - 3. # Present at each follow-up time point (i.e., Day 30, Discharge, Day 60, and Day 90); reasons for discontinuation/lost to follow-up.
 - 4. # Included in Final Analysis; reasons excluded from final analysis.
- iv. Withdrawal/follow-up

No follow-up was done for withdrawn participants. If a participant was withdrawn, then an attempt was made to obtain final prognosis information using clinical data available from the chart unless explicitly told not to do so by the participant.

v. Baseline Patient Characteristics

In addition to the screening variables described above, the variables below will also be summarized in a Baseline Characteristics Table. Continuous variables will be summarized using median and IQR while categorical variables will be summarized using counts and percentages. These statistics will be provided by condition (EMR Vs SOC) and as a whole.

- Barthel Index
- MADRS Score
- Gait Speed (Distance in meters and Time in seconds)
- 6-Minute Walk (Distance Ambulated, in feet)
- PANAS Score
- Short Blessed Test Score
- CIRS-G Score
- Clock Drawing Score

Analysis:

i. Outcome Definitions

- 1) Aim 1: Examine the effectiveness of EMR for improving functional outcomes in older adults admitted to SNFs for post-acute rehabilitation.

H1: EMR will improve functional recovery to a greater extent than standard-of-care rehabilitation.

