The primary measure employed for assessing functional improvement will be The Barthel Index. This index is a 10-item scale used to ascertain the degree of independence of normal daily activities. This will be done by taking the sum of these 10 items. A high score indicates a high degree of independence, and a score can range from 0 to 100.

- 2) Aim 2: Examine EMR's ability to overcome patient-level barriers to successful rehabilitation.

H2: The effectiveness of EMR for functional recovery will be greatest in: (a) patients with clinical depression; (b) patients with high levels of medical comorbidity; (c) patients with cognitive impairment.

Part (a) will be assessed using the MADRS, which is a 10-item scale used to assess for major depression. Each item is rated on a scale of 0 to 6, where a 6 is worse. The total score (i.e., sum of these 10 items) will be

used to assess for major depression and can range from 0 to 60.

Part (b) will be assessed using the CIRS-G, which is a 13-item scale used to assess for disease in all major body systems. Each item is rated on a scale of 0 to 4, with a 4 indicating severe impairment. The total score (i.e., sum of these 10 items) will be used to assess for medical comorbidity and can range from 0 to 52.

Part (c) will be assessed using the SBT Scores. The SBT is a 6-item scale used to assess for memory/concentration deficits. A total score, which is obtained after applying a weighting factor to each item then summing up the final item scores, can range from 0 to 28. A high score indicates impairment consistent with dementia.

ii. Analysis Methods

The primary outcome analysis for functional recovery will use a marginal model with time (baseline and discharge), condition (E-MR vs. SOC) and time x condition as fixed effects and with a covariance structure specified based on the Bayesian Information Criterion (BIC). Employing a marginal model allows for a more robust approach in the handling of missing data compared to the traditional ANCOVA model.

For H2 under Aim 2, each potential continuous moderator will be individually inserted into the primary model. The term of interest will be the time x condition x moderator interaction.

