The secondary analyses for Six-Minute Walk distance and Gait Speed will use a Mann-Whitney U Test to test for differences in means between groups. In addition, a Chi-Square test will be employed to test for independence between condition and the secondary outcome variable re-hospitalization. Finally, the outcome of self-reported function will use a marginal model using time (30, 60, and 90 days), condition and time x condition as fixed effects, with a covariance structure specified based on BIC.

Exploratory analyses will also test whether the effects of age, gender, race and site (i.e., Barnes Jewish Extended Care Vs Alexian Brothers Sherbrooke Village) altered the conclusions of the primary results as well as the conclusions of the moderator results.

Note: we will not look at the nesting of subjects within therapists who are then nested within site as this is not possible due to the inconsistency of assigning therapists to participants.

iii. Missing Data

We use a marginal model which accounts for missing data (no multiple imputation was used).

iv. Harms

An adverse event (AE) is any untoward medical occurrence in a subject temporally associated with participation in the clinical study or with use of the experimental agent being studied. An adverse finding can include a sign, symptom, abnormal assessment (laboratory test value, vital signs, electrocardiogram finding, etc.), or any combination of these.

AEs will be labeled according to severity (i.e., mild, moderate or severe), which is based on the AE's impact on the participant.

AEs will be categorized according to the likelihood that they are related to the study intervention or other study procedures (i.e., definitely unrelated, definitely related, probably related, or possibly related).

SAEs that are unanticipated, serious, and possibly related to the study intervention will be reported to the IRB, and NIMH in accordance with requirements. Unexpected fatal or life-threatening AEs related to the intervention will be reported to the NIMH Program Officer within 7 days. Other serious and unexpected AEs related to the intervention will be reported to the NIMH Program Official within 15 days. Anticipated SAEs will be handled in a less urgent manner but will be reported to the IRB in accordance with their requirements.

v. Statistical Software

All analyses will be performed using SAS and/or R.

vi. References

none

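### The pre-morbid Barthel Index is collected at baseline but used in no SAP analysis, leaving potential precision in the primary comparison unused

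*SAP*

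**What the plan says.** The primary outcome is the Barthel Index, a sum of ten items: "A high score indicates a high degree of independence, and a score can range from 0 to 100" (SAP, Analysis, i. Outcome Definitions). Under ii. Analysis Methods, the primary analysis "will use a marginal model with time (baseline and discharge), condition (E-MR vs. SOC) and time x condition as fixed effects", with the covariance structure chosen by BIC. For H2, each moderator is added to that model one at a time.

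The SAP's schedule of assessments lists "Barthel Index: Pre-morbid version" at baseline only. The protocol's baseline visit (F3) ends its list of assessments with "Readiness for Rehab, CIRS-G, Barthel Index: Pre-morbid version".

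The score does not appear again in the SAP. It is missing from the primary model, from the list of baseline characteristics, and from the sensitivity covariates: "Exploratory analyses will also test whether the effects of age, gender, race and site" changed the conclusions. The protocol's favored ANCOVA (G4) does not use it either; that analysis is described as "comparing the EMR and standard-of-care groups in change scores, covarying for baseline scores".

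**The concern.** The trial's hypothesis concerns recovery of function. The admission Barthel describes the disabled state. The pre-morbid Barthel describes the level the patient had before the event, and so bears on how much there is to regain. By its name it is a version of the outcome instrument itself, which makes it a natural candidate predictor of discharge function.

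If it does predict recovery, leaving it out keeps explainable variation in the residual. The confidence interval for the primary effect is then wider than it needs to be, and H1 is tested with less power than the collected data allow. The same holds in principle for the H2 interactions, although the documents give nothing from which to size that loss.

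**Working it through.** **Inputs from the documents.** N = 252 (protocol, opening summary); 1:1 allocation (E2, 2.d), so 126 per arm; d = 0.4, 80% power and two-sided alpha 0.025 (protocol G1; SAP, Sample Size); 5% significance level (SAP, Statistical Principles). Neither document gives the pre-morbid version's scoring, SD, completeness or correlation with any other measure. Every correlation below is therefore an assumption.

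**The plan's own sample size.** n per arm = 2(2.241 + 0.842)²/0.4² = 119, or 238 in total. A noncentral t calculation gives 242 and an ANCOVA F test with one covariate gives 241. None of these is 252. An unstated dropout of about 5% would come close (238/0.95 = 251). The gap is on the safe side and does not affect this point.

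**Step 1: what the stated model estimates.** Condition is free at baseline, so with complete data the time x condition term is the difference between arms in mean change. A covariate that is constant over time cancels out of within-patient change, so a main effect alone cannot move the estimate. I checked this on simulated complete data with N = 252, using five assumed correlation patterns, 400 trials each, and unstructured and compound-symmetric covariance. The estimate moved by less than 1e-15 in every trial.

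**Step 2: adding the covariate x time term.** Variance is multiplied by 1 − rho², where rho is the correlation of the pre-morbid score with change. Let P be pre-morbid, A admission and D discharge. With equal SDs for A and D,

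rho = (r_PD − r_PA) / √(2 − 2r_AD).

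**Step 3: power.** Take d = 0.4 as standardized to the contrast without the pre-morbid score. The normal approximation is Φ(0.4/√(1 − rho²) × √63 − z), with z = 2.241 at alpha 0.025 and 1.960 at alpha 0.05.

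| Assumed rho | Fall in variance | Power, alpha 0.025 | Power, alpha 0.05 |
|---|---|---|---|
| 0 | 0% | 0.825 | 0.888 |
| 0.2 | 4% | 0.841 | 0.900 |
| 0.3 | 9% | 0.861 | 0.914 |
| 0.4 | 16% | 0.889 | 0.934 |

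For rho = 0.3 at alpha 0.025: 0.4/√0.91 = 0.4193; 0.4193 × 7.937 = 3.328; 3.328 − 2.241 = 1.087; Φ(1.087) = 0.861.

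**Step 4: the ANCOVA or constrained-baseline form.** Here the relevant quantity is the partial correlation of P with D given A,

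(r_PD − r_PA·r_AD) / √((1 − r_PA²)(1 − r_AD²)),

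and its square is the further fall in variance relative to that same form without P. The two forms can give very different answers:

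| Assumed r_PA, r_PD, r_AD | Fall in SAP model (rho²) | Further fall in ANCOVA form (partial r²) |
|---|---|---|
| 0.3, 0.3, 0.5 | 0% | 3% |
| 0.5, 0.5, 0.5 | 0% | 11% |
| 0.3, 0.5, 0.5 | 4% | 18% |
| 0.2, 0.6, 0.4 | 13% | 34% |

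For the third row, rho = 0.2/√1 = 0.2, so rho² = 0.04. The partial correlation is 0.35/√(0.91 × 0.75) = 0.424, and its square is 0.18.

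Separately, moving from the change-score contrast to ANCOVA already reduces variance from 2 − 2r to 1 − r² (equal SDs, r = r_AD). At an assumed r of 0.5 that is 0.75 against 1.00, or 25% less, before the pre-morbid score is used.

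**The case against.** The strongest reply is that this is a preference. Randomization makes the unadjusted comparison valid, neither document promises this adjustment, and any omitted prognostic variable could be criticized in the same way. That stands, and it is why the point is minor. What sets this variable apart is that the trial already schedules it, apparently as a version of the outcome instrument, and states no use for it.

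The gain may also be nil. If the score correlates equally with admission and discharge Barthel (equal SDs), rho is zero and the stated model gains nothing. Patients who could not walk before hospitalization and those who normally live in long-term care are excluded, which may narrow the range of pre-morbid scores and weaken its correlations. That is an inference, but it counts against assuming a large rho.

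A reader might be tempted by four stronger readings:

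- **The precision is free and certain.** No correlation is reported, so the gain is only potential.
- **The squared partial correlation given admission Barthel gives the gain in the SAP's model.** It does not. That figure belongs to the ANCOVA or constrained-baseline form, as step 4 shows.
- **The score is available for every participant.** The documents show that it is scheduled, not that it is complete.
- **The primary test is biased.** Nothing here supports that.

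Finally, the SAP is marked final and already reports trial data: 22 SCIDs administered and 14 depression diagnoses. Replacing the primary model at that stage would be open to criticism. Those counts are pooled, so they do not show that outcomes had been seen by arm, but they make timing a real constraint on the fix.

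**Conclusion.** The point holds as a minor efficiency suggestion. A baseline measure with a plausible link to recovery is scheduled and then used in no SAP analysis, and the primary model adjusts for nothing beyond time and condition.

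In that model the benefit runs from nothing to a 16% fall in variance over assumed rho of 0 to 0.4. Power rises from about 82% to at most 89% at alpha 0.025, or from about 89% to at most 93% at the SAP's 5% level. These figures rest on complete data, N = 252, d = 0.4 and a correlation that the documents do not supply. In the ANCOVA or constrained-baseline form the benefit depends on a different correlation and may be larger. No gain for the H2 interactions has been computed.

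**What to change.** Add the pre-morbid Barthel and its interaction with time to the primary model, preferably with the baseline condition effect constrained to zero. An ANCOVA of discharge Barthel on admission and pre-morbid Barthel is the alternative. Use the same adjustment in the H2 models. A main effect alone is not enough in the model as written.

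State how the pre-morbid version is scored, give a simple rule for missing values (such as mean imputation of the covariate), and list the score in the baseline characteristics table.

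Make the adjusted model primary only if it is specified before outcome data are seen by arm, and keep the unadjusted model as a sensitivity analysis. If that point has passed, leave the stated model as primary and report the adjusted one beside it as a labelled sensitivity analysis.

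The cost is a few SAP sentences, no new data, and about one degree of freedom for the change contrast.

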Therefore, we created Enhanced Medical Rehabilitation (EMR) for older adults. A real-world adaptation of the science of behavior change, EMR is an integrated set of skills for physical and occupational therapists (PT/OT) that transform standard post-acute rehabilitation through: (1) a patient-directed, interactive approach (2) increased rehabilitation intensity (3) frequent feedback to patients on effort and progress. We developed training and supervision techniques so that PT/OTs carry out these skills with high treatment integrity.

In NIMH R34 pilot work, we found: (1) EMR is high-intensity and engaging: therapy by PT/OTs trained and supervised in EMR is greatly amplified in intensity and patient engagement compared to standard-of-care rehabilitation. (2) EMR improves functional and affective recovery: patients randomized to EMR had better improvement of function, physical performance, and positive and negative affect. (3) EMR overcomes barriers to rehabilitation: patients with depressive symptoms, cognitive impairment, and multiple medical comorbidities benefitted most from EMR relative to standard therapy.

We propose a randomized trial that will test EMR's benefits over standard-of-care rehabilitation for affective and functional recovery. Our aims are (1) examine the effectiveness of EMR for improving functional and affective outcomes in 252 older adults admitted to SNFs for post-acute rehabilitation, and (2) examine EMR's ability to overcome patient-level barriers (such as depression) to successful rehabilitation.

The innovation of this project is high: it is a novel application of theories of behavior change to improve both affect and function. It responds to NIMH strategic plan objective 3, "Develop new and better interventions for mental disorders that incorporate the diverse needs and circumstances of people with mental illness."

The public health significance is also high: recovery from disablement is a health issue of enormous human and economic significance. Success in this line of research will make rehabilitation more effective. Doing so would benefit all older adults in this sector of care but particularly those with depression, cognitive impairment, and other complications. This project addresses NIMH's goal of interventions to improve mental health and related health outcomes in real-world settings.

A2 Study Aims and Hypotheses

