2. PROMIS (Ability to Participate in Social Roles and Activities).
3. OARS IADL.

Process data: Measures of the dosage of intervention (# of EMR steps done in each therapy activity; PAT %; Rehab Participation Scale Score) before and after training.

Study Methods:

i. Trial Design:

This was a randomized, parallel-group trial where patients received either EMR or SOC therapy.

Patients who received EMR received therapy only from therapists who were trained and supervised in EMR. Their therapy sessions followed the EMR protocol. Otherwise, their SNF care did not differ from usual care.

Patients who received SOC received therapy only from PT/OTs (or assistants) who were not trained nor supervised in EMR. These therapists were monitored (videotaped or observed) but were not asked to do anything differently with their patients.

ii. Randomization:

Randomization (blocks...2 and 4 patients). was 1:1 to EMR or SOC with stratification by SNF site and by baseline depression status.

iii. Sample Size:

The sample size was based on 80% power to detect a Cohen's $d=0.4$ effect size on the ANCOVA difference in treatments at primary endpoint, based on a two-tailed $p<0.025$ (because two outcome measures are used). G*Power 3.1.2 was used for power calculations. A Cohen's $d=0.4$ is between "small" (0.2) and "medium" (0.5) effect sizes. Effect sizes for function were in the "large" range, $d=0.7-0.9$, but we acknowledge that these observed effect sizes are qualified by the small sample size, and it makes most sense to be more cautious regarding likely effect sizes in a full-scale study, hence our choice to power at $d=0.4$. Such an effect size is clinically relevant for the functional outcomes. *We will only examine affective recovery as an outcome for those who are "affectively impaired" to begin with; i.e., those with clinical depression at baseline; with this reduced N, we are powered at 80% for a $d=0.54$. This same power analysis would apply for any subgroup analysis of depressed; i.e., if we wish to demonstrate that EMR is effective both in the case of clinical depression and in "non-depressed" older adults.*

iv. Statistical Interim Analyses/Stopping Guidance:

Not applicable; we did not have any interim data analysis or early stopping plans.

v. Timing of Final Analysis:

All outcomes will be analyzed collectively.

vi. Timing of Outcome Assessments (including windows):

	Schedule of Assessments	SNF admit (baseline)	Day 7	Day 30	SNF discharg e	Day 60	Day 90

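### The primary marginal model leaves baseline means free by arm, so it tests mean change and not the ANCOVA difference to which the SAP's 80% power statement refers

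*SAP*

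**What the plan says.** - **Primary model.** SAP Analysis ii specifies a "marginal model with time (baseline and discharge), condition (E-MR vs. SOC) and time x condition as fixed effects", with the covariance structure chosen by BIC. No other terms are listed. The reason given is that this model "allows for a more robust approach in the handling of missing data compared to the traditional ANCOVA model".
- **Sizing.** SAP Study Methods iii states "80% power to detect a Cohen's $d=0.4$ effect size on the ANCOVA difference in treatments at primary endpoint". The sizing test is two-sided at 0.025, to allow for two outcomes. Power is not restated for the marginal model. SAP Statistical Principles i sets the level at 5%.
- **Sample size.** The number is in the protocol's opening summary, whose first aim is "improving functional and affective outcomes in 252 older adults admitted to SNFs for post-acute rehabilitation". The SAP gives no N.
- **Protocol method.** Protocol G4 says that the favoured method for the baseline to Day 30 "effects is the ANCOVA approach, comparing the EMR and standard-of-care groups in change scores, covarying for baseline scores". It adds that in the pilot data ANCOVA had at least as much power as a t test, a Wilcoxon test or a mixed model.
- **Strata.** SAP Study Methods ii describes 1:1 randomisation "with stratification by SNF site and by baseline depression status". Neither factor is in the primary model. Site appears only in the exploratory analyses, and depression only as the continuous MADRS moderator for H2. SAP Objectives reports 14 participants with a depression diagnosis.

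**The concern.** Baseline enters this model as an outcome and the condition main effect is unrestricted, so each arm has its own baseline mean. With two visits and complete data, the time x condition term is then the between-arm difference in mean change. That subtracts baseline with a fixed slope of 1, whereas ANCOVA estimates the slope. Randomisation makes the arms' true baseline means equal, and the model does not use that fact.

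Two things are at stake. Precision on the primary test is given up although the baseline data are in hand. And the only power statement in the SAP refers to a different analysis from the one specified.

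**Working it through.** **Inputs.** From the documents: d = 0.4, 80% power, two-sided alpha 0.025, 1:1 allocation, N = 252 (126 per arm). Not in the documents, so assumed: ρ of 0.3, 0.5 or 0.7; equal SDs σ at baseline and discharge; no dropout, with 15% as a sensitivity case. Whether d is scaled to the ANCOVA residual SD or to the raw SD is also unstated, so both are shown.

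**1. The plan's own figure.** n per arm = 2(z₀.₉₈₇₅ + z₀.₈₀)²/d² = 2(2.241 + 0.842)²/0.16, which rounds up to 119, or 238 in total. The t-based ANCOVA calculation gives 121 per arm, or 242. Power at 252 is 82.5% (normal) or 82.1% (t). The planned N therefore slightly exceeds what an ANCOVA contrast with d on the residual SD needs.

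**2. What the specified model tests.** In simulated complete data, the time x condition estimate equalled the difference in mean change to within 1e-14.

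**3. Variance.** Per participant, Var(change) = 2(1−ρ)σ² and Var(ANCOVA) = (1−ρ²)σ². The ratio is 2/(1+ρ). With unequal SDs s₀ (baseline) and s₁ (discharge), the change score's excess variance is (s₀ − ρs₁)². So it is never the more precise, and it ties only when the slope of discharge on baseline is 1.

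**4. Power, 126 per arm, alpha 0.025 (noncentral t).** On the residual SD, effective d for the SAP model is 0.4·√((1+ρ)/2). On the raw SD it is 0.4/√(2(1−ρ)) for the SAP model and 0.4/√(1−ρ²) for ANCOVA.

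| | ρ = 0.3 | ρ = 0.5 | ρ = 0.7 |
|---|---|---|---|
| Variance ratio | 1.54 | 1.33 | 1.18 |
| Equivalent ANCOVA N = 252(1+ρ)/2 | 164 | 189 | 214 |
| Residual SD: effective d, SAP model | 0.322 | 0.346 | 0.369 |
| Residual SD: power, SAP model | 62.0% | 68.9% | 74.9% |
| Residual SD: power, ANCOVA | 82.1% | 82.1% | 82.1% |
| Residual SD: N for 80%, SAP model | 370 | 320 | 284 |
| Raw SD: power, SAP model | 66.6% | 82.1% | 96.7% |
| Raw SD: power, ANCOVA | 85.8% | 92.0% | 98.5% |

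Simulation of the residual-SD case (4,000 runs per cell) gave 62%, 68% and 75% for the SAP model against 82% for ANCOVA.

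**5. Alpha 0.05.** On the residual SD the SAP model has 72.2%, 78.2% and 83.0%, against 88.5% for ANCOVA. On the raw SD it has 76.2%, 88.5% and 98.3%.

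**6. Where the SAP model reaches 80%.** On the residual SD, ρ must be at least about 0.91 (alpha 0.025) or 0.57 (alpha 0.05). On the raw SD, about 0.48 or 0.36 is enough.

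**7. Missing discharge values.** With 15% removed completely at random (residual SD, alpha 0.025), ANCOVA had 74% power. The SAP model fitted by likelihood had 57%, 61% and 66%, and a completers' change-score t test had 54%, 60% and 65%. Keeping baseline-only participants therefore adds about 1 to 2.5 points and does not close the gap.

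**The case against.** **The shortfall depends on unstated quantities.** This stands. If d is on the raw SD, the SAP model keeps at least 80% over much of the plausible range of ρ. A reader might infer that the trial is underpowered as analysed; the documents do not support that, because they give neither ρ nor the SD.

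**A change-score analysis is legitimate.** This stands. Under randomisation it is unbiased with valid type I error. Protocol G4 lists mixed models among the permitted methods and calls ANCOVA only its favoured one. The SAP's sizing sentence can also be read as a record of the original design. None of this makes the stated power apply to the model specified.

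**The missing-data reason has substance.** It does, in part. Baseline-only participants let the likelihood correct each arm's discharge mean for dropout related to baseline, which a completers' change score does not do. Calling the argument empty would go too far. But ANCOVA is already valid when missingness depends on baseline and arm, and likelihood handling does not require a free baseline: a marginal model with a common baseline mean has it too.

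**The strata are a side issue.** Largely true. A reader might infer that leaving out site and depression is what makes this a change-score test, or that it inflates type I error. Neither follows. The free baseline creates the change-score property. With complete data, adding a time-constant site or depression term to the SAP model would not move time x condition; a factor x time term is needed. Omitting prognostic strata usually makes a test conservative. Site is checked in the exploratory analyses, and 14 diagnosed participants leave little to gain from the depression term.

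**Conclusion.** The point holds as one of efficiency and of a mismatched power statement, not of bias. As specified, the primary test is the difference in mean change when data are complete. Its variance is 1.54, 1.33 or 1.18 times that of ANCOVA at ρ of 0.3, 0.5 or 0.7, assuming equal SDs at the two visits. At N = 252 and alpha 0.025 the cost is about 20, 13 or 7 power points on the residual-SD reading (82.1 less 62.0, 68.9 or 74.9). On the raw-SD reading it is about 19, 10 or 2 points (85.8 less 66.6, 92.0 less 82.1, 98.5 less 96.7). Whether power falls below 80% cannot be settled from the documents. The change should be made because it gains precision from data already collected and puts the power statement on the right analysis.

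**What to change.** 1. For the baseline and discharge Barthel, constrain the arms to a common baseline mean: drop the condition main effect and keep time and time x condition. Use an unstructured covariance in place of BIC selection. With two visits it has only three parameters, and too simple a structure would misstate the baseline-discharge slope on which the constrained estimate depends. ANCOVA of discharge Barthel on baseline is an acceptable alternative.
2. Add the randomisation strata (site, and depression status as used at randomisation) with their time interactions, or as covariates in the ANCOVA.
3. State the ρ and the SD behind d = 0.4, and restate power for the model actually used. Reconcile the 0.025 in the sizing text with the 5% level in Statistical Principles at the same time; that is a separate discrepancy.
4. If the specified model has already been run, report the constrained model as a labelled sensitivity analysis.

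The Day 30, 60 and 90 visits need not be added: the primary contrast is baseline to discharge, and the gain comes from the baseline constraint. The cost is a few lines of SAP text and code, with no new data.
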